The summary of event rates will be based on survival analysis of time to first event based on an index date defined for each treatment group with appropriate censoring rules applied for those who do not experience an event by end of follow-up period including those who die, those who are lost to follow-up (eg, via migration out of the country as documented in the data source), or end of study period.

The feasibility of more formal comparative analyses to evaluate safety events of interest and obtain hazard ratios that adequately adjust for potential confounders will be assessed in the interim reports. Since the size of the once daily somatropin-treated comparator group is

expected to be much larger than the somatrogon-treated group, statistical power will be limited by the uptake of somatrogon.

Milestones: Data collection is planned to start on 15 June 2024 and end on 15 June 2032. The first interim report is planned to be submitted within three years of EU approval of somatrogon, taking into account the lag in data availability in respective data sources. Subsequent interim reports are planned for every 2 years thereafter. The final study report planned for submission will take place within 6 months from the end of data collection.

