6. MILESTONES

Milestone	Planned date	
Registration in the EU PAS register	Prior to start of data collection	
Start of data collection ^a	15 June 2024	
End of data collection ^b	15 June 2032	
Interim report 1	15 December 2024	
Interim report 2	15 December 2026	
Interim report 3	15 December 2028	
Interim report 4	15 December 2030	
Final study report	15 December 2032	

EU: European Union; PAS: post authorisation study.

a. For studies with secondary data collection, the start of data collection is defined as the planned date for starting data extraction for the purposes of the primary analysis.

b. For studies with secondary data collection, the end of data collection is defined as the planned date on which the analytical dataset will be first completely available; the analytic dataset is the minimum set of data required to perform the statistical analysis for the primary objective(s).

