9. RESEARCH METHODS

9.1. Study design

This is a population based cohort study using routinely collected electronic healthcare data in France, Spain, Sweden, and the UK, during a study period of February 2022 to February 2032. Table 1 summarizes these data sources and their capabilities of addressing research objectives. The study population will be comprised of paediatric patients (ie, patients from 3 years to below the age of 18) who initiate once weekly somatrogon following registration of the product in the EU and UK, and an internal comparator population of paediatric patients who initiate treatment with daily somatropin accrued during the same time period as the somatrogon treated patients.

Table 1. Summary of study objectives and country-specific databases that have data to address them.

	Système National des Donnees de Sante (SNDS)	Longitudinal Patient Database (LPD) in Spain	Sweden Growth Hormone Registry and national health and demographic registers	The Health Improvement Network (THIN)
Primary objective	yes	yes	yes	yes
Secondary objective 2a	yes*	yes	yes	yes***,†
Secondary objective 2b	no	no	yes	no
Secondary objective 2c	yes	yes	yes	yes
Secondary objective 2d	yes**	yes	yes	yes [†]

^{*}not for medication errors as weight is not collected in this database.

† not for all immunogenicity clinical endpoints.

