9.2.3. Index Date and Follow-Up

The index date will be the date of the first filled prescription/dispensing of somatrogon or once daily somatropin as recorded in the data sources. The patients will be followed from the index date to whichever of the following that occurs first:

- Primary or secondary safety event of interest (follow-up time will be from the index date to the date of the event, at which the patient will be censored for that particular event of interest. Follow-up will continue for the other safety events of interest)
- Death
- Lost to follow-up (eg, via migration out of the country as documented in the data source(s)), or
- End of the study follow-up

The study will span a 10-year study period, throughout which patients can accrue and will be evaluated in 2 stages. First, patients will be accrued within the first 5 years and followed for a minimum of 5 and up to 10 years to evaluate long-term safety events of interest, Figure 1. Second, in sensitivity analyses, all patients that accrue after the 5-year mark, and therefore, with less than 5 years of follow-up, will be analyzed both separately and together with the study population. (Section 9.7.2.4)

Figure 1. Patients Inclusion and Follow-up

Inclusion of patients prescribed/dispensed with at least 1 dose of somatrogon or once daily somatropin

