 - Hospital data: date of admission, ward type, admission following ER visit (yes/no), date of discharge, discharge diagnoses (1 principal, 1 related and up to 50 associated), DRG, procedures, drugs invoiced in addition to the DRG, external consultation at hospital, and costs.

- Outpatient prescription data: number of prescriptions reimbursed, prescriber's specialty, and costs.
- o Pharmaceutical information:
 - Outpatient (community pharmacy): brand, generic name, Anatomical Therapeutic Chemical (ATC) code, CIP code ('Code Identifiant de Présentation', for each specific packaging), size, strength.
 - Inpatient (hospital: list 'en sus', retrocession list): brand, generic name, ATC code, UCD code ('Unité Commune de Dispensation', for the smallest unit of dispensation [eg, pill, vial]), dosage form and strength, amount administered.

Lag in data availability for SNDS varies from 1 month (outpatient data) to 12 months (hospital data).

• Spain-The LPD database contains anonymized electronic data collected from approximately 3,000 office-based primary and secondary physicians, representing about one million patients (covering approximately 3% of the national population). The patient population is representative of the Spanish population according to geographic coverage, and age and gender distribution, as provided by the Instituto Nacional de Estadística (INE). Healthcare contacts done outside of the national health system are not captured (private sector).

The electronic medical records (EMR) collect medical information from the practice management software used by the physician during patients' office visits for recording their daily patient interactions in EMRs. The panel of contributing physicians is maintained as a representative sample of the primary care and specialist physician population in Spain. Panel physicians volunteer to make available anonymized, patient-level information from their practices for clinical research purposes.

The patient identifier is unique through all general practitioner and specialist practices. Data are captured directly from patients' EMRs, with no intervention being made to collect or complete the data. The LPD is therefore, secondary data collected in a non-interventional way, reflecting routine clinical practice. In-hospital treatment administration, including for somatrogon (or somatropin), is not available in the LPD database, only prescription at discharge is collected in these situations.

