- Demographics: age, sex, place of residence, place of birth, citizenship, immigrant status, immigration date, race/ethnicity.
- Diagnoses made in in- and out-patient care, recorded by ICD codes, as well related admission and discharge dates. Incident cancer diagnosis is morphologically confirmed.
- Ambulatory prescription and dispensations: date, prescriber profession, brand name, formulation, package, DDD, dispensed amount, and expenditures. All drugs are classified according to the ATC classification system. [Wettermark et al 2007]
- O Growth data: Ethiology for GH treatment, co-morbidity and other hormone treatments, birth length and weight as well as gestational age, years on and start of growth hormone treatment, parental height, growth rate during first treatment year, weight and height at start and at puberty onset, age and final height, IGF-1 and GH maximum from 24-hr growth hormone profiling. [Emilsson et al 2015 for a general overview of treatment registries]

The lag time in diagnosis/prescription fill to the incorporation of data into the national registers is between 1 month and 1 year depending on the register. There is a 15-month lag between clinical data being entered into the system and the data being available for analysis (eg, the Cancer Registry has a delay of 15 months). The implication of this is that complete data for 2022 is available in the registers at the end of 2023. Additionally, there is typically a waiting time of 10-12 months between the time of data order submission and delivery of the data by the register holders.

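### With the dataset due in June 2032, the stated data lags rule out the 5-year minimum follow-up for French hospital diagnoses and Swedish registers, so the follow-up behind Tables 4 and 5 needs restating

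*Protocol*

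**What the plan says.** - **Study period and follow-up.** Section 9.1 runs the study "during a study period of February 2022 to February 2032". Section 9.2.3 states that "patients will be accrued within the first 5 years and followed for a minimum of 5 and up to 10 years". The assumptions under Tables 4 and 5 repeat this: 10 years in total, 5 of accrual, and at least 5 years for the last patient enrolled.
- **Dataset date.** Sections 4 and 6 put the end of data collection at 15 June 2032. For secondary data, Section 6 defines this as the "planned date on which the analytical dataset will be first completely available".
- **Lags (Section 9.4).** France: 1 month for outpatient data, up to 12 months for hospital data. Sweden: 1 month to 1 year depending on the register, and then "There is a 15-month lag between clinical data being entered into the system and the data being available for analysis", with the Cancer Registry as the example. Also for Sweden, "there is typically a waiting time of 10-12 months between the time of data order submission and delivery of the data", introduced as an addition to the lag. Spain and the UK: 1 month.
- **Where the lag is acknowledged.** Section 9.4 says each report will reflect the data available at database lock. The abstract takes the lag into account for the first interim report. Neither statement alters the 5-year minimum, the June 2032 date or the sample-size thresholds.
- **Thresholds (Section 9.7).** By data source and without pooling, a comparison is made only with at least 1,305 somatrogon patients (neoplasms) or 2,344 (type 2 diabetes). The justification is that HR 3.00 is then detectable with 80% power.

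**The concern.** Four months separate the end of the study period from the date of the complete dataset. A 1-month lag fits in that gap; lags of 12 and 15 months do not. The stated minimum follow-up therefore cannot be observed for outcomes taken from French hospital data or the lagged Swedish registers.

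Two things depend on it. The descriptive rates in those sources rest on less follow-up than the protocol promises. The thresholds for the comparative analysis are patient counts whose 80% power assumes the full 10-year design, so a threshold could be met when its stated justification no longer holds. Because sources are not pooled, one source cannot make up for another.

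**Working it through.** **1. Dates.** Count back from 15 June 2032. February to June 2032 is 4 months, so observable study length is T = 10 + 4/12 − lag in years. Minimum follow-up for a February 2027 entrant is T − 5.

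- France, 12 months: data to June 2031, 8 months short of February 2032. T = 9.33, minimum 4.33 years.
- Sweden, 15 months: data to March 2031, 11 months short. T = 9.08, minimum 4.08 years.
- Sweden, 15 + 10 to 12 months: data to March–May 2030, 21 to 23 months short. T = 8.08–8.25, minimum 3.08–3.25 years.

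Section 9.4 also says that 2022 data are complete at the end of 2023, which is nearer a 12-month lag. That gives Sweden at best the French figure, still below 5 years.

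**2. Reproducing the plan.** Inputs from Section 9.5: comparator rate h = 0.0009 per year, HR 3, 1:1 allocation, uniform accrual over 5 years, 5% annual loss (l = −ln 0.95 = 0.0513). Sidedness is not stated; two-sided 0.05 reproduces the table.

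Event probability per patient, with c = h + l:
P = (h/c) × [1 − (e^(−c(T−5)) − e^(−cT)) / (5c)]

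At T = 10, P = 0.00555 (comparator) and 0.01655 (somatrogon), sum 0.02210.

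Events needed, with p = HR/(1 + HR) = 0.75:
d = [(1.96 × 0.5 + 0.8416 × √(0.75 × 0.25)) / 0.25]² = 28.92

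N per group = 28.92 / 0.02210 = 1,308 (stated 1,305). With h = 0.0005 the same steps give 2,347 (stated 2,344). The model matches the plan.

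**3. Shortening T only.** Expected events are E = 1,305 × (sum of the two P). Power = Φ[(0.25√E − 0.98) / 0.433]. Person-years per patient = (1/l) × [1 − (e^(−l(T−5)) − e^(−lT)) / (5l)].

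| | Plan | France, 12 mo | Sweden, 15 mo | Sweden, 25–27 mo |
|---|---|---|---|---|
| T (years) | 10 | 9.33 | 9.08 | 8.25–8.08 |
| Person-years per patient | 6.19 | 5.73 | 5.55 | 4.94–4.81 |
| Events at 1,305 | 28.8 | 26.7 | 25.9 | 23.1–22.5 |
| Power for HR 3.00 | 80% | 76% | 75% | 70–68% |
| N for 80%, neoplasms | 1,308 | 1,414 | 1,459 | 1,637–1,679 |
| N for 80%, diabetes | 2,347 | 2,536 | 2,617 | 2,938–3,014 |
| Detectable HR at 1,305 | 3.00 | 3.10 | 3.15 | 3.31–3.35 |

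**4. Relaxing Table 4's other assumptions.** With k comparators per somatrogon patient, p₀ = 1/(1+k) and p = HR/(HR+k). The comparator's P is multiplied by k in E, and
Power = Φ[(√E (p − p₀) − 1.96√(p₀(1−p₀))) / √(p(1−p))].

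- 1:2, 5% loss. France: E = 1,305 × (2 × 0.00514 + 0.01532) = 33.4, power 90%. Sweden: 89% (15 months) and 84–85% (25–27 months).
- 1:10, 5% loss: 96%, 96% and 93–94%.
- 1:1 with 1% annual loss (my assumption for minimal loss): 83%, 81% and 74–75%.

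**The case against.** The strongest reply concerns power. Section 9.7 expects the comparator group to be an order of magnitude larger than the somatrogon group, and Section 9.9 expects minimal loss in France and Sweden. Step 4 bears this out: 1:2 allocation alone restores power above 80% in every scenario. Loss of 1% a year at 1:1 does so for France and for the 15-month Swedish lag. A reader might infer that the comparison will be underpowered; the documents do not show that. What is wrong is the stated basis of Tables 4 and 5. In addition, only a conditional secondary analysis is affected. Sweden may never reach 1,305 somatrogon patients, given about 1,700 paediatric somatropin patients in 2019, and the French count is unavailable.

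The dates also carry some slack. The longer Swedish gap assumes that the order wait follows the lag, as the wording suggests but does not settle. Twelve months is the upper bound for France, and some chronic diagnoses arrive through long-term disease registration, which may be faster. Not every Swedish register lags by 15 months.

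Finally, a reader might infer that rates will be understated by 10 to 20%, or understated more for somatrogon. Neither is supported. The first needs person-time to run past the outcome data; nothing in the protocol plans that, and a source-specific cut-off is ordinary SAP content. The second needs later somatrogon accrual, whereas the protocol accrues both groups over the same period and assumes a constant rate.

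None of this restores the 5-year minimum for the lagged outcome data.

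**Conclusion.** The point holds as an internal conflict. The February 2032 study end, the 15 June 2032 dataset, the lags in Section 9.4 and the 5-year minimum cannot all be true for French hospital diagnoses and the lagged Swedish registers. The shortfall is about 8 months in France and 11 months in Sweden, or 21 to 23 months in Sweden if lag and order wait add up.

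Under Table 4's assumptions as written, the cost at 1,305 patients is about 4 percentage points of power in France and 5 (or 10 to 12) in Sweden. Person-years per patient fall by about 7%, 10% and 20 to 22%. These figures depend on 1:1 allocation and 5% annual loss, both of which the protocol itself expects to be pessimistic. The conclusion is that follow-up and thresholds are misstated, not that the study is underpowered or its rates biased.

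**What to change.** 1. In Section 9.2.3, end follow-up for each source and outcome at the last date to which the register supplying that outcome is complete. Without such a rule, person-time could run past the period in which events are observable and understate rates.
2. State the expected total and minimum follow-up per source: about 9.3 and 4.3 years for French hospital diagnoses; about 9.1 and 4.1 for Sweden, or 8.1–8.25 and 3.1–3.25 if the order wait adds. Say which Swedish reading applies, and reconcile the 15-month lag with the statement about 2022 data.
3. Recompute Tables 4 and 5 and the 1,305 and 2,344 thresholds for that follow-up, with realistic allocation and loss.

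Alternatively, reconcile the end-of-data-collection milestone with the lags for the slower sources.

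Items 1 to 3 cost wording and a recalculation, and the thresholds need not rise once allocation and loss are realistic. Moving the milestone is optional. It would delay the final report and need the regulator's agreement, since the study is a post-authorisation commitment.

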9.5. Study size

All somatrogon-treated paediatric patients in all data sources during the study accrual period will be included in the study. Table 2 shows the estimated incidence rate of the primary safety events of interest in somatropin-treated paediatric patients from previous GHD studies.

Table 2. Incidence Rate of the Primary Safety Events of Interest in Somatropintreated Paediatric Patients from Previous GHD Studies

Study	Event	Incidence Rate per 1,000 Person-years	Person-years of Exposure Needed to Observe One Event
KIGS ^a	Neoplasms	0.89	1,124
	Cancer	0.18	5,556
	Diabetes mellitus type 2	0.016	62,500
NCGS ^b	Neoplasms	NA	NA
	Cancer	0.19	5,264
	Diabetes mellitus type 2 (includes 8 unclassified diabetes mellitus cases) ^c	0.14	7,143
	Diabetes mellitus type 2 (excludes 8 unclassified diabetes mellitus cases) ^c	0.10	10,000
GeNeSIS ^d	Neoplasms	NA	NA
	Cancer	0.21	4,762
	Diabetes mellitus type 2	0.52	1,923

GHD-Growth hormone deficiency; NA-Not applicable.

- c. Bell J, Parker KL, Swinford RD, Hoffman AR, Maneatis T, Lippe B. Long-term safety of recombinant human growth hormone in children. J Clin Endocrinol Metab. 2010 Jan;95(1):167-77. doi: 10.1210/jc.2009-0178. Epub 2009 Nov 11. PMID: 19906787.
- d. GeNeSIS (Genetics and Neuroendocrinology of Short Stature International Study; Eli Lilly, Indianapolis, IN, USA); $19\,054$ children with no recorded history of cancer. Patient years of exposure $\sim 64,784$.

Table 3 shows estimated prevalence of paediatric GHD patients in each selected country, and estimated number of somatropin-treated paediatric patients in each database. Preliminary feasibility assessment of data in the Swedish nationwide and regional registers from 2008 to 2019 indicates that there was approximately 4,000 patients treated with somatropin each year, with 1700 patients in 2019 estimated to be paediatric patients. In the UK THIN database from 1995-2020, there were approximately 3,375 patients treated with somatropin

PFIZER CONFIDENTIAL

a. Pharmacoepidemiological database with data of children treated with recombinant human GH (Kabi International Growth Study Genotropin; Pfizer Inc., New York, NY). Enrolled patients 1987-2012. IGHD: N=39116, Patient years of exposure=126,754. Data on file.

b. Open-label, multicenter, post-marketing surveillance study, the National Cooperative Growth Study (NCGS), to monitor the safety and efficacy of its rhGH products in children with growth disorders (Genentech, Inc). 1985-2006. N=54,996. Patient years of exposure=192,345.

with 20% (650 patients) estimated to be paediatric patients. In Spain, from 2013-2022, there were approximately 700 patients treated with somatropin, of which 642 received a first dose as a paediatric patient. Similar information from France was unavailable.

Table 3. Estimated Prevalence of Paediatric GHD in each Country, and Estimated Count of Somatropin Patients in each Database

Country	Approx. paediatric population size in selected countries (Millions) ^a	Approx. paediatric GHD prevalent cases in selected countries ^b	Datab ase	Nationa l coverag e (%)	Total approx. number of unique somatropi n patients in database	Total approx. number of unique somatropin paediatric patients in database	Period of coverage of database
France	6.71	1,676	SNDS	99	Unavailable	Unavailable	2009-2019
Spain	9.35	2,337	LPD	3.2	700	642	2013-2022
UK	6.66	1,666	THIN	6	3,375	~650	1995-2020
Sweden	2.20	550	Natio nal registr ies	100	~4,000 per year	~1,700	2008-2019

GHD-Growth hormone disease; Approx-Approximate; LPD-Longitudinal Patient Database; SNDS-The French administrative health care database (Système Nationale des Données de Santé); THIN- The Health Improvement Network.

Sample size calculations were undertaken to estimate the number of patients required to assess each of the primary safety events of interest. All sample size calculations were conducted using PASS software version 20.0.3, with Logrank test.

Sample size calculation to estimate the number of patients required to assess the risk of neoplasms

Sample size calculations were undertaken to estimate the number of patients required to assess the risk of neoplasms. Table 4 presents detectable hazard ratios among somatrogon

PFIZER CONFIDENTIAL

a. Paediatric population (<18 years) approximated to 20% of 2019 population. https://ec.europa.eu/eurostat/documents/2995521/11081093/3-10072020-AP-EN.pdf/d2f799bf-4412-05cc-a357-7b49b93615f1 https://www.populationpyramid.net/europe/2019/

b. Prevalence of childhood GHD in Europe approximated to be 1/4,000. Orso M, Polistena B, Granato S, et al. Pediatric growth hormone treatment in Italy: a systematic review of epidemiology, quality of life, treatment adherence, and economic impact. PLoS One 2022; 17(2): e0264403. https://doi.org/10.1371/journal.pone.0264403.

treated patients compared with once daily somatropin-treated patients. Assuming a range of 1,305 - 20,000 patients exposed to somatrogon, the minimum hazard ratios (HRs) between treatment groups that could be detected with at least 80% power at the 5% significance level are summarized. Based on the estimates presented in Table 4, assuming 0% annual rate of switching from somatrogon-treated patients to once daily somatropin-treated patients, and 0% annual rate of switching from once daily somatropin-treated patients to somatrogon treated patients, and a neoplasm incidence rate of 0.9/1000 person-years in once daily somatropin-treated paediatric patients (Table 2), sample sizes of 1,305 and 20,000 somatrogon-treated patients would allow for HRs of 3.00 and 1.41, respectively, to be detected between the somatrogon-treated and once daily somatropin-treated groups. Comparative analyses for neoplasms will be performed if there are $\geq 1,305$ patients in the somatrogon-treated group, which would allow for an HR of 3.00 or higher to be detected between somatrogon and once daily somatropin-treated groups. The occurrence of switching will inevitably require a greater sample size and higher thresholds to inform the conduct of comparative analyses.

Table 4. Minimum Detectable Hazard Ratios Among Somatrogon-treated Patients Compared with Once Daily Somatropin-treated Patients with 80% Power, alpha = 0.05, 10-year Study with 5 Years Uniform Accrual, 5% Loss to Follow Up Per Year in Somatrogon-treated group - Neoplasms

Incidence rate per 1,000 person-years of neoplasms in once daily somatropin treated group	Sample size of patients in once daily somatropin treated group (N1)	Sample size in Somatrogon population (N2)	Hazard Ratio
0.9	1,305	1,305	3.00
0.9	2,000	2,000	2.54
0.9	4,000	4,000	2.01
0.9	5,000	5,000	1.89
0.9	10,000	10,000	1.60
0.9	20,000	20,000	1.41

Table 4 assumptions:

- $\alpha = 0.05$
- Power=0.8
- Different somatrogon-treated patient population sizes: n=1,305, 2,000, 4,000, 5,000, 10,000, 20,000
- 1:1 ratio between somatrogon-treated patient population and comparator group of once daily somatropin-treated patients
- Estimated incidence rate of neoplasms in comparator group of once daily somatropintreated patients: 0.9 per 1,000 person-years
- 10-year total study duration (5 years patient accrual, and minimum 5 years follow-up for last enrolled patient)

- Constant rate of accrual
- 5% annual loss to follow up among somatrogon-treated patients, and 5% annual loss to follow up among once daily somatropin-treated patients
- Assuming 0% annual rate of switching from somatrogon-treated group to once daily somatropin-treated group, and 0% annual rate of switching from once daily somatropin-treated group to somatrogon-treated group.

Sample size calculation to estimate the number of patients required to assess the risk of diabetes mellitus type 2

Sample size calculations were undertaken to determine the number of patients required to assess the risk of diabetes mellitus type 2. Given the wide variability of results obtained in the estimation of the incidence rate of diabetes mellitus type 2 (Table 2), sample size calculations were repeated assuming incidence rate for diabetes mellitus type 2 of 0.1/1,000 person-years, and 0.01/1,000 person-years. Table 5 presents detectable hazard ratios among somatrogon-treated patients compared with once daily somatropin-treated patients. Assuming a range of 2,000 - 20,000 patients exposed to somatrogon, the minimum HRs between treatment groups that could be detected with at least 80% power at the 5% significance level are summarized. Based on the estimates presented in Table 5, assuming 0% annual rate of switching from somatrogon-treated patients to once daily somatropin-treated patients, and 0% annual rate of switching from once daily somatropin-treated patients to somatrogon treated patients, and incidence rate of 0.5/1,000 person-years in once daily somatropintreated paediatric patients (Table 2), sample sizes of 2,000 and 20,000 somatrogon-treated patients would allow for HRs of 3.21 and 1.57, respectively, to be detected between the somatrogon-treated and once daily somatropin-treated groups. Comparative analyses for diabetes mellitus type 2 will be performed if there are $\geq 2,344$ patients in the somatrogon treated group, which would allow for an HR of 3.00 or higher to be detected between somatrogon and once daily somatropin-treated groups. The occurrence of switching will inevitably require a greater sample size and higher thresholds to inform the conduct of comparative analyses.

Table 5. Minimum Detectable Hazard Ratios Among Somatrogon-treated Patients Compared with Once Daily Somatropin-treated Patients with 80% Power, alpha = 0.05, 10-year Study with 5 Years Uniform Accrual, 5% Loss to Follow Up Per Year in Somatrogon-treated group – Diabetes Mellitus Type 2

Incidence rate per 1,000 person-years of diabetes mellitus type 2 in once daily somatropin treated group	Sample size of patients in once daily somatropin treated group (N1)	Sample size in Somatrogon population (N2)	Hazard Ratio
0.5	2,000	2,000	3.21
0.5	2,344	2,344	3.00
0.5	4,000	4,000	2.44

Table 5. Minimum Detectable Hazard Ratios Among Somatrogon-treated Patients Compared with Once Daily Somatropin-treated Patients with 80% Power, alpha = 0.05, 10-year Study with 5 Years Uniform Accrual, 5% Loss to Follow Up Per Year in Somatrogon-treated group – Diabetes Mellitus Type 2

Incidence rate per 1,000 person-years of diabetes mellitus type 2 in once daily somatropin treated group	Sample size of patients in once daily somatropin treated group (N1)	Sample size in Somatrogon population (N2)	Hazard Ratio
0.5	5,000	5,000	2.26
0.5	7,368	7,368	2.00
0.5	10,000	10,000	1.84
0.5	15,000	15,000	1.67
0.5	20,000	20,000	1.57
0.1	2,000	2,000	7.59
0.1	4,000	4,000	5.04
0.1	5,000	5,000	4.47
0.1	10,000	10,000	3.21
0.1	11,688	11,688	3.00
0.1	15,000	15,000	2.71
0.1	20,000	20,000	2.44
0.1	36,765	36,765	2.00
0.01	10,000	10,000	12.06
0.01	20,000	20,000	7.58
0.01	25,000	25,000	6.61
0.01	50,000	50,000	4.47
0.01	75,000	75,000	3.65
0.01	100,000	100,000	3.21
0.01	116,811	116,811	3.00
0.01	367,475	367,475	2.00

Table 5 assumptions:

- $\alpha=0.05$
- Power=0.8
- Different somatrogon-treated patient population sizes: n=2,000, 2,344, 4,000, 5,000, 7,368, 10,000, 11,688, 15,000, 20,000, 25,000, 36,765, 40,000, 50,000, 75,000, 100,000, 116,811, 367,475
- 1:1 ratio between somatrogon-treated patient population and comparator group of once daily somatropin-treated patients
- Estimated incidence rate of diabetes mellitus type 2 in comparator group of once daily somatropin-treated patients: 0.5 per 1,000 person-years, 0.1 per 1,000 person-years of the person
- 10-year total study duration (5 years patient accrual, and minimum 5 years follow-up for last enrolled patient)

PFIZER CONFIDENTIAL

- Constant rate of accrual
- 5% annual loss to follow up among somatrogon-treated patients, and 5% annual loss to follow up among once daily somatropin-treated patients
- Assuming 0% annual rate of switching from somatrogon-treated group to once daily somatropin-treated group, and 0% annual rate of switching from once daily somatropin-treated group to somatrogon-treated group.

